6.3. Measures Taken to Minimize/Avoid Bias

6.3.1. Randomization

A randomization plan will be used to allocate subjects into experimental groups, per the study priorities described in Section 6.2. In addition, as of Version 5.0, ten replacement subjects will be enrolled into Group 6. A fixed random allocation will ensure that the groups are balanced in size at the end of experiment.

Designated study personnel (excluding the principal investigator [PI] and other investigators) will fill the vaccine cohorts as potential subjects successfully complete the screening process and are deemed eligible to participate by the PI (or another designated investigator). For the purposes of this study, the groups will be defined as follows, and each subject will receive one dose of vaccine on Days 0, 28, and 56.

Group 1 (12 subjects): HTNV by ID EP

Group 2 (12 subjects): HTNV by IM EP

Group 3 (12 subjects): PUUV by ID EP

Group 4 (12 subjects): PUUV by IM EP

Group 5 (12 subjects): HTNV/PUUV by ID EP

Group 6 (22 subjects): HTNV/PUUV by IM EP

6.3.2. Blinding

Blinding is not applicable and will not be used in this protocol.

6.4. Investigational Product

The investigational products that will be administered using the TDS-IM V1.0 or TDS-ID EP device are the HTNV, PUUV, and HTNV/PUUV DNA vaccines given as a single injection. These investigational products were manufactured by Ajinomoto Althea, Inc., San Diego, California. Table 5 presents a summary description of the investigational products. See the Investigator's Brochure and the Pharmacy Manual for further product information and for detailed vaccine preparation and administration instructions.

Table 5: Investigational Product

Product Name	HTNV DNA Vaccine pWRG/HTN-M(co)	PUUV DNA Vaccine pWRG/PUU-M(s2)	HTNV/PUUV DNA Vaccines
Dosage Form	Liquid	Liquid	Liquid
Unit Dose/Injection Volume	ID: 0.6 mg/0.2 mL IM: 3.0 mg/1.0 mL	ID: 0.6 mg/0.2 mL IM: 3.0 mg/1.0 mL	ID: 1.2 mg (0.6 mg each)/0.2 mL IM: 6.0 mg (3.0 mg each)/1.0 mL
Route of Administration	ID or IM injection deltoid region in alternate arms, if possible	ID or IM injection deltoid region in alternate arms, if possible	ID or IM injection deltoid region in alternate arms, if possible
Physical Description	Clear, colorless solution	Clear, colorless solution	Clear, colorless solution
Manufacturer	Ajinomoto Althea, Inc. San Diego, CA 92121	Ajinomoto Althea, Inc. San Diego, CA 92121	Ajinomoto Althea, Inc. San Diego, CA 92121
Lot Number	1-FIN-2118	1-FIN-2117	1-FIN-2118/1-FIN-2117 ^a
Product Indication	Intended for human use in adults as a prophylactic measure against HFRS	Intended for human use in adults as a prophylactic measure against HFRS	Intended for human use in adults as a prophylactic measure against HFRS

^a A pre-mixed lot of HTNV and PUUV does not currently exist. These will be mixed at the clinical site's pharmacy prior to administration.

6.4.1. Investigational Product Packaging and Labeling

Label information for the vaccines and saline are reproduced below (manufacturer information and/or a combination of additional over-label not to obscure the manufacturer label will be used):

Single use Hantaan vials are labeled as follows:

pWRG/HTN-M(co) Plasmid DNA in PBS Buffer
Part No.: 4-FF-1016 Lot No.: 1-FIN-2118
Vol.: 0.5 mL/vial Conc.: 6.0 mg/mL
Mfg. Date: 14Jan15 Store at -20°C ± 10°C
Caution: New Drug – Limited by Federal
(or United States) Law to Investigational Use
Manufactured by Ajinomoto Althea, Inc.,
[name]
The Geneva Foundation, Contract V-1674-01

Box ____ of ____ Vials Per Box ____

Single use Puumala vials are labeled as follows:

pWRG/PUUV-M(s2) Plasmid DNA in PBS Buffer
Part No.: 4-FF-1015 Lot No.: 1-FIN-2117
Vol.: 0.5 mL/vial Conc.: 6.0 mg/mL
Mfg. Date: 20Feb15 Store at -20°C ± 10°C
Caution: New Drug – Limited by Federal
(or United States) Law to Investigational Use
Manufactured by Ajinomoto Althea, Inc.,

[name]
The Geneva Foundation, Contract V-1674-01

Box _____ of _____ Vials Per Box _____

[figure not shown]
Saline material used as diluent, will be used and CoA, CoC will be provided for each lot utilized.

The vaccines may be transported to the University of Maryland's Investigational Drug Services Pharmacy using dry ice and other transport media whose average temperature is below the label ranges. Sponsor experience has shown that these vaccines may be transported and stored at temperatures below label (down to $-80^{\circ}\text{C} \pm 10^{\circ}\text{C}$) for no more than 24 hours without compromising product potency or safety. Likewise, the vaccine manufacturer has successfully stored and transported plasmid vaccines at temperatures down to $-80^{\circ}\text{C} \pm 10^{\circ}\text{C}$ without issue.

6.4.1.1. Ichor TriGrid™ Delivery System

The TDS-IM V1.0 and TDS-ID investigational devices are supplied by Ichor Medical Systems, Inc. The TDS devices utilize the in vivo application of electrical fields to enhance the intracellular delivery of agents of interest in a targeted region of tissue (EP). Before the study starts, study personnel will be trained on device usage by Ichor personnel, and this training will be documented. During this study, this device will be operated according to the TDS-IM V1.0 and TDS-ID Instructions for Use documents. Each TDS device consists of 3 parts: A pulse stimulator, an integrated applicator, and a single-use application cartridge (Figure 1). Further information on the devices can be found within the TDS-IM V1.0 and TDS-ID Investigator's brochure.

Figure 1: TDS-IM V1.0 and TDS-ID Delivery Devices

6.4.2. Investigational Product Storage

The HTNV DNA and PUUV DNA vaccines will be stored at $-20^{\circ}\text{C} \pm 10^{\circ}\text{C}$. Saline will be stored at room temperature conditions, $22.5^{\circ}\text{C} \pm 2.5^{\circ}\text{C}$. Sponsor experience has shown that these vaccines may be transported and stored at temperatures below label (down to $-80^{\circ}\text{C} \pm 10^{\circ}\text{C}$) for at least 24 hours without compromising product potency or safety. Likewise, the vaccine

manufacturer has successfully stored and transported plasmid vaccines at temperatures down to -10°C to -90°C (-80°C ± 10°C) without issue. Temperature excursions within these parameters during shipment/transportation of the vaccines will not incur a protocol deviation.

6.4.3. Investigational Product Preparation

The University of Maryland's Investigational Drug Services (IDS) will prepare the vaccines for administration. A supplementary document entitled "Manual of Procedures" has been supplied to the University of Maryland CVD describing the procedures to be followed when preparing the vaccines for administration. Briefly, the products to be administered in Groups 1-4 will be mixed with saline to bring them to the correct concentration for dosing; these groups are all single vaccine component groups. For the groups that are administered combination product (Groups 5 and 6), the HTNV and PUUV vaccines will be mixed with each other at a 1:1 ratio to bring them to the correct concentration. The supplementary document describes the products, their storage and management, procedures for product preparation, the volumes of each component to be combined, the supplies to be used (eg, syringes or other device-specific requirements), and any data collection forms for recording procedures as they are performed.

6.4.4. Investigational Product Accountability

The sponsor's representative is responsible for overseeing the distribution of the investigational product to the study site. In this study, investigational product refers to both the vailed vaccine, diluent, and the single-use cartridges associated with the TDS-IM V1.0 and TDS-ID devices. The sponsor's representative has delegated drug accountability responsibility for this product to The University of Maryland's Investigational Drug Services (IDS) under the supervision of the PI; however, the sponsor's representative has ultimate responsibility for product accountability.

After the investigational product is distributed, the IDS is responsible for and will maintain logs of investigational product receipt, storage, reconstitution, accountability by subject, and investigational product remaining before final disposition. At the UMB CVD, the logs will be maintained in the accountability files within the office of the CVD. The PI may delegate, in writing, this responsibility to another individual, but the PI is ultimately responsible for the investigational product and its proper storage upon receipt at the study site until it is transferred back to the sponsor's representative or designee, or is destroyed as directed by the sponsor's representative.

All vials (unused, partially used, and spent) will be retained by the study staff for accountability. Any IP that experiences a temperature excursion will be placed in quarantine status and the Sponsor will be notified of the temperature excursion. The sponsor will determine the disposition of the quarantined IP. No vials should be destroyed or disposed of without specific instructions from the sponsor's representative and as stipulated by local, state, and federal regulations. This occurs after the study monitor has completed the final accountability inspection. The disposition records will account for all remaining investigational products.

All unused or partially used investigational product and empty vials will be destroyed when directed by the sponsor's representative and as stipulated by local, state, and Federal regulations. This occurs after the study monitor has completed the final accountability inspection.

The single-use application cartridges for the EP device will only be retained by the study product administrator for accountability if there is an error or issue at the time of administration,

otherwise the cartridge will be discarded appropriately. Any cartridge that is found to malfunction or otherwise function incorrectly will be recorded as such so that it can be assessed by the manufacturer for the cause of said dysfunction. The disposition records will account for all remaining single use cartridges.

Following completion of vaccinations, the TDS-IM V1.0 and TDS-ID reusable devices will be returned to Ichor.

6.5. Duration of Subject Participation

The expected duration of individual enrolled subject participation will be approximately 5 months including the screening period.

6.6. Study Halting Criteria

Further enrollment and study vaccinations will be halted for SMC review/recommendation if any of the following are reported:

- Any subject experiences a study product-related SAE from the time of the study product administration through the subject's last study visit.
- Any subject experiences laryngospasm, bronchospasm, or anaphylaxis within 1 day after administration of study product that is considered related to study product.
- Two or more subjects experience generalized urticaria (defined as occurring at more than 2 body parts) within 3 days after administration of study product that is considered related to study product.

This trial will also be halted for SMC review/recommendation if, within 7 days after administration of any study vaccination, any of the following occurs:

- Two or more subjects experience a Grade 3 unsolicited AE in the same MedDRA system organ class (captured by preferred term) after administration of study product that is considered related to study product and not resolved or improved to lower grade within 2 days.
- Two or more subjects experience the same Grade 3 solicited local adverse event that is considered related to study product and not resolved or improved to lower grade within 2 days.
- Two or more subjects experience the same Grade 3 solicited systemic adverse event that is considered related to study product and not resolved or improved to lower grade within 2 days.
- Two or more subjects experience the same Grade 3 laboratory adverse event that is considered related to study product.

Grading scales for solicited local (application site) and systemic (subjective and quantitative) AEs are included in Section [10.5](#) and [Appendix C](#).

Grading scales for clinical safety laboratory adverse events are included in Section [10.5](#) and [Appendix C](#).

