The first study enrollment activities will involve selection and randomization of volunteers as sentinels for Groups 2 and 4, and then subjects for the remainder of the Group 2 and 4 cohort. The sentinel subjects for Groups 2 and 4 (n = 2 per group, or 4 total) will be vaccinated and evaluated for 48 hours prior to dosing the remainder of Group 2 and 4 (n = 10 per group, or 20 total). After the first dose for all subjects in Groups 2 and 4 has been successfully completed and none of the halting criteria are met, then the first dose will be given to 2 sentinel subjects in Group 6 (n=2 , total of 2 subjects) on the same day, and those 2 subjects will be followed for 48 hours as per the Sentinel Group Halting Rules. The SRC will meet and evaluate the safety data collected in the 48-hour period post-vaccination for sentinels in Group 6. If the SRC finds that the halting rules have been met (Section 6.6.1.1), the PI will notify ORA PSSO within 24 hours. An SMC meeting will be held to conduct a review of clinical and laboratory safety and reactogenicity data. After the meeting, the SMC will make its recommendations in writing regarding continuation, modification, or termination of the clinical trial. If the recommendation is to proceed, enrollment, randomization, and vaccination (Day 0) of the remaining volunteers in Group 6 (n=10 per group). The first dose will be given to 2 sentinel subjects in Group 5 (n=2, total of 2 subjects) on the same day and those 2 subjects will be followed for 48 hours as per the Sentinel Group Halting Rules. The SRC will meet and evaluate the safety data collected in the 48-hour period post vaccination for sentinels in Group 5. If the SRC finds that the halting rules have been met (Section 6.6.1.1) the PI will notify ORA PSSO within 24 hours. A SMC meeting will be held to conduct a review of clinical and laboratory safety and reactogenicity data. After the meeting, the SMC will make its recommendations in writing regarding continuation, modification, or termination of the clinical trial. If the recommendation is to proceed, enrollment, randomization, and vaccination (Day 0) of the subjects in Groups 1 and 3 (n=12 per group, total of 24 subjects) will commence. Subjects in Groups 1 and 3 will be evaluated for the 48-hours post-vaccination for any halting criteria on the Day 2 clinic visit (Table 4). After completion of enrollment and first vaccination for Groups 1 and 3, the remaining subjects for Group 5 and ten Group 6 replacements (total of 20 subjects) may be enrolled, randomized and vaccinated (Day 0), provided that the enrollment of these 20 subjects can be completed within 4 months (see randomization schedule in Appendix B). Subjects are expected to complete a total of 11 visits (not including screening). There will be a 6 month follow-up after the final injection (Day 220). Overall study duration is expected to be approximately 8 months.

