8.1.4. Follow-Up Visits

There will be 9 follow-up visits: Day $2 + 1$ day, Day 14 ± 2 days, Day 30 ± 1 day, Day 42 ± 2 days, Day 58 ± 1 day, Day 70 ± 2 days, Day 84 ± 4 days and Day 140 ± 7 days and D220 Phone Call ± 14 days

The following procedures will be performed during each follow-up visit (some exceptions):

- Review of subject's medical history (including concomitant medications and AE) since previous visit
- Directed physical examination (injection site) if indicated based on the subject's interim medical history

- Take resting vital sign measurement including oral temperature, heart rate, respiratory rate, and systolic and diastolic blood pressure. Subjects must not eat or drink anything hot or cold, or smoke within 10 minutes prior to taking oral temperature.
- Review and collect memory aids (Days 14, 42, 70)
- Collect approximately 12.5 to 72.5 mL (depending on the scheduled visit day, see [Table 4](#)) of whole venous blood for the determination of:
 - CBC (WBC, Hb, platelets) with differential (Days 14, 42, and 70 only)
 - Glucose, Cr, AST, ALT, total bilirubin, (Days 14, 42, and 70)
- Collect blood for determination of HTNV- and PUUV-specific antibodies as measured by PsVNA assay (Days 84 and 140)
- Collect approximately 50 mL of blood for future research on Day 84 only
- Collect blood sample for determination of pregnancy test (Day 140 only)
- Perform ECG as last assessment of cardiac normality (Day 140 only)

Day 140 will be the final scheduled in-clinic visit for all subjects

Serious Adverse Event Final Telephone Follow Up Visit

There will be a scripted telephone follow up visit conducted at Day 220 ± 14 days.

- Review and collection of serious adverse events occurring since last visit conducted at Day 140.

Early Termination Visits

If a subject leaves the study early (see also Section [7.5](#)), procedures pertaining to Day 140 in the follow-up visit section (Section [8.1.4](#)) will be followed:

- Review of subject's medical history (including concomitant medications and AE) since previous visit
- Directed physical examination (injection site) and resting vital signs check (oral temperature (no recent hot or cold beverages or smoking), heart rate, respiratory rate, and systolic and diastolic blood pressure)
- Review and collection of any remaining memory aids
- HTNV- and PUUV-specific antibodies (PsVNA50 for final visit)
- Serum sample collection for determination of pregnancy test
- Perform ECG

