8.4. Subject Compliance and Memory Aid Completion

Subjects who are unable to follow the study requirements and arrive at study visits will be withdrawn from the study at the PI's discretion. Poor compliance with study visits would include the inability to come to a scheduled study visit within window on 2 or more occasions.

Withdrawal procedures for such instances are detailed in Section [7.5](#).

Following each injection, subjects will be provided a memory aid (ie, fillable diary card) and instructed in its use. On a daily basis during the 14-day period after each injection subjects will evaluate and record any local or general symptoms (eg, fever, myalgia, and malaise) they experience (see Section [10.3.2](#)). To more accurately account for possible fevers, subjects will be given an oral thermometer, instructed on its use, and asked to take and record their temperature daily for the first 14 days after each injection. Also, subjects will be asked to record local reactions at the injection site (such as erythema, edema, bruising, and pain) for 14 days after each injection. To more accurately account for the size of any such reactions, subjects will be given a ruler and instructed on how to use it. Memory aids will be reviewed by an investigator at follow-up visits during the 14-day post-injection period. Memory aids will be collected from the subjects at the 14-day post-injection visit. If memory aids are not completed or returned, an investigator will review the AEs that occurred during that time frame to the best of the subject's recollection. Subjects will be instructed on the use of the memory aid and encouraged to fill it out as directed; if it is not completed or not brought to a study visit by 28 days following each dose, then a protocol deviation will be documented. The maximum intensity reported by the subject whether recorded on the memory aid or verbally reported to the study staff will be recorded in the eCRF as an AE with a grade and relationship as determined by the assessing investigator.

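### The clinical Grade 3 halting rules count events for 7 days after a dose, but no contact or call-in covers Days 4 to 11, so an event not volunteered is learned of about 5 to 10 days after it counts

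*Protocol*

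**What the plan says.** Protocol section 6.6 opens with "Further enrollment and study vaccinations will be halted for SMC review/recommendation if any of the following are reported" and then lists the rules that apply "if, within 7 days after administration of any study vaccination, any of the following occurs". Three of these are clinical: a Grade 3 unsolicited event in the same system organ class, the same Grade 3 solicited local event, or the same Grade 3 solicited systemic event. Each needs two or more subjects, relatedness to study product, and no improvement within 2 days. SAP section 4.1.1 uses the same 7-day window and adds no contact.

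Safety contacts come from Table 4 and section 8.1.4. After dose 1 they are Day 2 (+1) and Day 14 (±2). After doses 2 and 3 they are Days 30 and 58 (±1), then Days 42 and 70 (±2). Section 10.6.1 has adverse events assessed at study visits. Section 8.4 has subjects fill in the memory aid daily for 14 days and states: "Memory aids will be reviewed by an investigator at follow-up visits during the 14-day post-injection period". Collection is at the 14-day visit. The only scheduled telephone contact is at Day 220, for serious events.

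For Groups 1 and 3, which have no sentinels of their own, section 6.2 adds a check: "Subjects in Groups 1 and 3 will be evaluated for the 48-hours post-vaccination for any halting criteria on the Day 2 clinic visit".

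**The concern.** A halting rule acts only on events the site knows about. These three rules give weight to onset as late as Day 7, and the 2-day persistence condition moves the point at which an event counts to as late as Day 9. The plan's scheduled looks fall at Day 2–3 and then at Day 12–16. Nearly all of the period the rules govern therefore has no planned observation, and the daily diary that would show the event stays with the subject.

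If two subjects had the same persistent Grade 3 reaction on Days 3 to 7 and neither mentioned it, the criterion would be met while the site went on dosing others. The stake is how promptly the rule protects subjects still to be dosed. Solicited-event data are not lost, because the diary is collected in the end.

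**Working it through.** The documents state no detection delay, so there is no figure to reproduce. The check is day arithmetic on the visit windows.

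**Inputs**
- Qualifying window: onset through Day 7 after a dose (section 6.6).
- Persistence: not improved within 2 days (section 6.6).
- Contacts after dose 1: Day 2–3, then Day 12–16; nominally Days 2 and 14 (Table 4, section 8.1.4).
- Contacts after doses 2 and 3, with dosing on the nominal day: 30 ± 1 − 28, or 58 ± 1 − 56, gives 1 to 3 days after the dose; 42 ± 2 − 28, or 70 ± 2 − 56, gives 12 to 16 days after.

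**Formulas**
- Countable day = onset + 2.
- Delay = day of next scheduled contact − countable day.

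**Results for an event that starts after the early visit and is not volunteered**

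| Case | Shortest delay (onset Day 7) | Longest delay (onset just after the early visit) |
|---|---|---|
| Dose 1, nominal visits | 14 − (7 + 2) = 5 days | 14 − (2 + 2) = 10 days |
| Dose 1, with windows | 12 − (7 + 2) = 3 days | 16 − (2 + 2) = 12 days |
| Doses 2 and 3, with windows | 12 − (7 + 2) = 3 days | 16 − (1 + 2) = 13 days |

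Section 6.6 can also be read as requiring the 2 days of persistence to fall inside the 7. The last qualifying onset is then Day 5, and the dose 1 delay with windows is 12 − (5 + 2) = 5 days at least and still 12 at most. The conclusion does not depend on the reading.

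**Does other text close the gap?**
- Section 8.1.3 has staff teach subjects to complete the memory aid; it does not say to call if an entry is severe.
- Section 8.4 accepts symptoms reported verbally, without a trigger or a deadline.
- Section 10 promises continuous review of data, which cannot reach a diary still at home.
- Section 14.2.2 pays for unscheduled visits but does not prompt one.
- Section 10.1.3 has the Safety Review Committee review sentinels at 48 hours. Section 10.1.4 has the Safety Monitoring Committee meet annually, at study end, or when a rule is met or a concern is raised. Neither finds an unreported event.

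The Grade 3 laboratory rule has no persistence condition and is outside this calculation.

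**The case against.** The strongest objection is that a call-in may already exist. The memory aid, the Manual of Procedures and the consent form are where one would normally sit, and none is among the documents reviewed. A reader might infer that the trial has no such instruction at all. The documents do not support that; they show only that the protocol and SAP text does not contain one.

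Second, these delays describe scheduled detection. A subject who cannot carry out daily activities, or whose temperature is 39.0 °C or more, may well call unprompted. The 12- and 13-day figures also combine the earliest early visit with the latest diary visit, so 5 to 10 days is the fairer summary.

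Third, the risk is limited:
- Severe soreness with the IM device resolved by 48 hours (section 4.5.1.1), and severe fatigue came within 24 hours of dosing and resolved by the next day (section 4.5.1.2).
- Related systemic events with the ID device were Grade 1 or 2 (section 4.5.1.2). The one completed ID study gave at most 0.3 mg (section 4.4.2.4), against 0.6 and 1.2 mg here, so this reassures only in part.
- The affected subject's diary is in hand by Day 12–16, before the next dose at Day 28 ± 4. A Grade 3 event in the 7 days after vaccination without alternative etiology is a listed ground to stop that subject's dosing (section 7.5).

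All of this stands, and it limits the weight of the point. Three stronger readings do not stand.

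- *A missing condition at the last stage.* Section 6.2 makes one step conditional, "After the first dose for all subjects in Groups 2 and 4 has been successfully completed and none of the halting criteria are met", but opens another with "After completion of enrollment and first vaccination for Groups 1 and 3, the remaining subjects for Group 5 and ten Group 6 replacements" and names no halting condition there. A reader might infer that the last 20 subjects could be dosed despite a known halt. The Synopsis halting text and section 6.6 bar further enrollment and vaccination once any rule is met, at every step. The difference is one of drafting.
- *A count of subjects exposed.* The number dosed during the delay depends on a calendar the documents do not give. It is 0 if all are dosed on one day. At the slowest pace allowed for the last 20 (4 months taken as 120 days), it is 20 × 3/120 = 0.5 to 20 × 12/120 = 2.0. If the other 22 subjects of Groups 1 and 3 were spread evenly over 28 days, it is 22 × 3/28 = 2.4 to 22 × 12/28 = 9.4. These are assumptions, and no one figure should be quoted.
- *A need for a fixed hold before the last stage.* Section 6.2 orders the groups to meet contract time limits. A hold would trade against that, and the documents do not show it to be necessary.

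**Conclusion.** The mismatch is real on the protocol and SAP text. An unvolunteered event with onset after the early visit and by Day 7 is learned of 5 to 10 days after it becomes countable with visits on nominal days after dose 1. The range is 3 to 12 days with visit windows, and 3 to 13 days after doses 2 and 3 if dosing is on the nominal day. These figures assume that the event persists as the rule requires and that the subject reports it only at the next scheduled contact.

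The consequence is a slower halt while others may be dosed, by a number that cannot be determined. Given the early onset of known severe reactions and the protection before the affected subject's next dose, this is a change the plan should make, not a fundamental fault in the design. Confidence is moderate, because a document not supplied may already contain the instruction.

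**What to change.** In section 8.4 and on the memory aid, tell subjects to call the site the same day for any entry that reaches Grade 3 level in Appendix C, through Day 7 after each dose. Put the thresholds in lay terms, for example: prevents daily activity, any narcotic pain reliever, temperature of 39.0 °C or more, redness or swelling over 10 cm. The site calls back 2 days later to check persistence, which is the condition the halting rules use. The investigator still assigns grade and relatedness. If the memory aid, Manual of Procedures or consent form already says this, cite it in sections 6.6 and 8.4 instead.

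The cost is a protocol wording change, one line on the memory aid, and a few calls with one call-back for each report. It adds no visit and no wait between stages. The staging text in section 6.2 needs no change on this account.
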